STU#:

PROTOCOL TITLE: *Evaluation of a mobile health application to improve patient satisfaction and outcomes after urethroplasty: a prospective randomized controlled trial*

PRINCIPAL INVESTIGATOR:

[name]
 Department of Urology
 [contact]
 [contact]

VERSION DATE:

1.1

STUDY SUMMARY:

Investigational Agent(s) (Drugs or Devices)	Mobile Medical App
IND / IDE / HDE #	n/a
Indicate Special Population(s)	 Children  Children who are wards of the state  Adults Unable to Consent  Cognitively Impaired Adults  Neonates of Uncertain Viability  Pregnant Women  Prisoners (or other detained/paroled individuals)  Students/Employees
Sample Size	80
Funding Source	Department of Urology, Northwestern University Urology Care Foundation
Indicate the type of consent to be obtained	 Written  Verbal/Waiver of Documentation of Informed Consent  Waiver of HIPAA Authorization  Waiver/Alteration of Consent Process
Site	 Lead Site (For A Multiple Site Research Study)  Data Coordinating Center (DCC)
Research Related Radiation Exposure	 Yes  No
DSMB / DMC / IDMC	 Yes  No

STU#:

OBJECTIVES:

Our objective is to create a custom urethroplasty specific mobile application that will guide patients through the perioperative period for urethroplasty. This application will include preoperative reminders, informational videos, postoperative instructions, and an interactive guide for common postoperative concerns such as bladder spasms, wound healing, gross hematuria, and wound and catheter issues. We will conduct a prospective, randomized controlled trial over a one-year period assessing the effectiveness of our application on perioperative outcomes and patient satisfaction for patients undergoing urethroplasty at our institution.

Aim 1: The primary study aim is to improve patient satisfaction, education, and patient reported outcome measures after urethroplasty. All enrolled patients will complete a urethroplasty specific PROM survey, the Urethral Stricture Symptom and Impact Measure (USSIM), as well as the Patient-Reported Outcomes Measurement Information System 29-item profile (PROMIS-29 v2.0) preoperatively, two weeks after catheter removal, and again at three months after surgery. Three months after surgery patients will also complete a decision regret scale. Patients enrolled with the application will complete an overall assessment of GetWell Loop at the end of the study.

Aim 2: The second aim of the study is to decrease patient phone calls and messages due to improved patient education and troubleshooting provided by the interactive guide. Prospective chart review will be conducted on all patients enrolled in the study to evaluate the number of MyChart messages and phone calls.

Aim 3: The final aim is to decrease emergency department visits and improve postoperative outcomes. Postoperative complications will be rated on the Clavien-Dindo classification. Emergency department visits will be assessed by prospective chart review and patient interviews. Overall healthcare costs will be extrapolated based on the outcomes of emergency department visits.

STU#:

BACKGROUND:

Urethral stricture disease is fibrosis within the urethra that leads to significant narrowing of the urethral lumen. Strictures can occur from traumatic, iatrogenic, inflammatory, infectious, or idiopathic etiologies. Urethroplasty is the most effective and durable treatment for urethral stricture. However, perioperative care for urethroplasty is complex. Preoperative counseling can be challenging as the anatomy can be quite foreign to the layperson, thus the description of the procedure as well as the associated risks and benefits can be difficult to understand. Indeed, this appears to be a universal problem within surgery and multiple studies have highlighted poor patient comprehension and recall from standard preoperative counseling. Preoperative care can also be cumbersome, with patients in urinary retention managed with a urethral Foley requiring conversion to a suprapubic tube to allow for a period of urethral rest. Preoperative urine cultures are also required, and many patients will have a positive urine culture requiring antibiotic treatment prior to surgery.

Postoperatively, all patients will have a urethral catheter for 1-4 weeks depending on the repair. More complex strictures may require buccal mucosa graft and even local tissue flaps such as a gracilis muscle flap. At our institution, many patients undergo same-day discharge or are admitted for one night, limiting time for in person postoperative teaching. These attributes underscore the importance of patient education as they may generate patient questions and anxiety.

Studies have shown a discordance between patient and physician perception regarding success after urethroplasty surgery. As a result, there has been growing interest in patient reported outcome measures (PROM) as a marker for success after urethroplasty. However, PROM surveys are time and resource intensive to capture.

Mobile health applications have the potential to improve patient education, quality of life, and postoperative outcomes after surgery. They are also a way to capture PROM in a more reliable and efficient manner. Within the field of urology, mobile health applications have been created for perioperative prostatectomy and cystectomy care. However, no mobile health application has been created for urethroplasty, and there has not been a randomized controlled trial regarding their efficacy within this space.

Mobile health applications are low-cost, accessible, and scalable resources that have been gaining popularity in recent years. Most patients own a smartphone regardless of socioeconomic status. Most mobile health applications are geared towards chronic illness and primary prevention, however interest in surgery specific mobile health applications is growing. A survey regarding willingness to use mobile health applications after a hypothetical surgery scenario conducted on 800 New York State residents by Abelson et al, found that 80.6% of respondents reported willingness to wear a tracker on their wrist and 74.3% were willing to fill out a daily survey after surgery. Notably, older respondents were less likely to own a smart phone but had similar willingness to participate in mobile health technologies if they did own one.

STU#:

Within urology, Belarmino et al conducted a feasibility study for the use of a mobile health application after robotic assisted radical prostatectomy. 20 patients were recruited preoperatively and completed a baseline PROM survey. Their application did not include preoperative counseling but was rather focused on postoperative care including reminders to perform Kegel exercises, ambulate, and hydrate. Men were asked to complete the same PROM survey weekly after catheter removal. All respondents reported that the push reminders were useful and 93% found the app easy to use. Importantly, they also found that the PROM response rates were significantly higher than those for mail and email surveys and comparable to phone surveys.

Metcalfe et al conducted a study in 2019 implementing an application for cystectomy perioperative monitoring. 20 patients were enrolled in the pilot trial and given a tablet with the preloaded application as well as a step monitor and vital sign equipment. Their study did include 14 preoperative educational videos on topics such as "Ileal conduit versus Neobladder" and "Comprehensive Care Pathway". All participants viewed the videos and 93% averaged more than one view per video.

Notably, both these studies were feasibility studies and no study within urology thus far has evaluated the effectiveness of these mobile health applications for patient education or compared them to the standard of care.

We will conduct a prospective, randomized controlled trial assessing the effectiveness of a mobile health application on perioperative outcomes and patient satisfaction for patients undergoing urethroplasty.

STUDY ENDPOINTS:

Primary endpoint: Improve patient satisfaction, education, and patient reported outcome measures after urethroplasty.

Secondary endpoint: decrease patient phone calls, chart messages, ER visits, and improve complication rates.

STUDY INTERVENTION(S) / INVESTIGATIONAL AGENT(S):

We will conduct this study in partnership with GetWell Loop, a mobile medical application designed by GetWell Network. We plan to work with GetWell to develop a custom build plan for a urethroplasty specific perioperative patient education application. Eligible patients will be randomized to one of two arms: standard care pathway and the mobile health (mHealth) pathway.

GetWell Loop MMA details:

Purpose of the app:

The purpose of the app is to guide patients through the perioperative period surrounding urethroplasty. The application will include preoperative reminders, informational videos, postoperative instructions, and an interactive guide for common postoperative concerns such as bladder spasms, wound healing, gross hematuria, and wound and catheter issues. We will be utilizing the survey data collected from the app to determine if PROMs improved with the convenience and accessibility of this app.

STU#:

The app is appropriately suited for adults 18 and older and is aesthetically easy to read/navigate and easy to understand.

App functionality:

GetWell Loop can be accessed via URL link (www.getwellnetwork.com) to their website using any computer with Internet capability. It can also be accessed in app format and can be downloaded onto iOS or Android devices via Google Play and Apple App Store. The app is free and there is no cost to the participant. Participants will use their own devices for the study. Participants without mobile phone/computer capability to utilize GetWell Loop will be excluded from the study. GetWell has technical support available on their website with Frequently Asked Questions as well as on demand technical support via a Customer Support [contact]) for any participants with app related technical issues. When a device's operating system is updated, the app's functionality will not be impacted. However, GetWell Loop's mobile app does require iOS 12.4 or later or Android 5.0+. The proposed care plan will last for 90 days and patients enrolled in the care plan will automatically be removed at the end of the study. When the study is over or when a participant withdraws, we will personally contact the participant to provide instructions on removal of the application.

Participant/user support:

Participants will be trained to use the app during their initial in person visit if they choose to sign up for the study and are randomized to one of the mHealth arms. In addition, the app provides a tutorial for usage when first downloaded. Participants have access to GetWell's technical support Frequently Asked Questions on their website as well as on demand technical support via a Customer Support [contact]) for any participants with app related technical issues. The app will be monitored via patient feedback and data collection. Participants will be able to message providers with questions regarding the app or regarding their care through GetWell Loop and via Epic myChart. We will monitor survey data collected weekly to ensure that patients are able to complete surveys without issue.

Obtaining consent and the app's Terms of Service:

We will obtain written consent during a patient's initial urethroplasty appointment. Participants will not be consented via the app. The consent form is in-line with GetWell's Terms of Service, which are located on their website and uploaded along with this protocol. Data ownership is outlined in the Privacy Policy, which is also available on GetWell's website and attached with this protocol. All data collected and provided by participants is owned by GetWell. The Terms of Service will be summarized in the IRB consent form in a participant friendly manner. The Terms of Service are compliant with research regulations and local/state/federal law. We will plan to monitor for changes or updates to the Terms of Services by asking the GetWell developer team to email us when updates are made.

STU#:

Privacy and confidentiality protections:

Research data including patient demographic, survey and medication adherence data will be collected in GetWell. All data from GetWell Loop will be stored anonymously with nonidentifiable patient identifiers in the GetWell Loop U.S. based Google Compute Cloud data center, which can be downloaded remotely by the research team. Data will then be compiled and prospectively maintained in an encrypted REDCap database through our institution. Data will be accessible only to authorized members of the study team. GetWell will have access to raw data collected from mobile surveys but will not have access to research data collected from Epic to determine qualitative/quantitative improvements in urethral stricture disease. GetWell Loop does require a username and password for everyone. Usernames are generated by the user. If a participant forgets their username and/or password, there are links on the GetWell Loop login page titled "Forgot password" and "Forgot username?" in which participants can receive a username/password reset sent to their email. Data from this study may be submitted back to the FDA in the future including patient demographic, survey and medication adherence data will be collected in GetWell.

[figure not shown]
Risks related to app use:

GetWell's Privacy Policy is available on their website and attached with this protocol. Privacy and confidentiality risks include that while encryption is used for certain information using TLS (transport layer security), no method of transmission over the internet or electronic storage is 100% secure. If the app does not work as intended or malfunctions, participants can contact the Customer Support [contact]). GetWell Network has a Chief Information Security Officer who oversees the app for potential security risks. One of the lead team members of this project will monitor and receive notifications from the secure messaging portal if there are any concerns on a weekly basis. Patients will also have the option to ask care-related concerns through Epic MyChart. All information in this study is kept confidential between the study team and the participants, and no third parties will be involved.

PROCEDURES INVOLVED:

We will conduct a prospective, randomized controlled trial assessing the effectiveness of a mobile health application on perioperative outcomes and patient satisfaction for patients undergoing urethroplasty over a 12-month period. Experimental design including inclusion and exclusion criteria is outlined in **Figure 1**. Patients will undergo a two-stage consent process and a non-blinded randomization technique. Our institution performs 80-100 urethroplasty procedures a year. Our goal is to enroll 80 patients, 40 patients per arm. To reduce attrition, financial incentive will be provided after completion of the final study survey (obtained at three months postoperatively) with a \$100 Amazon gift card. If enrollment is significantly lower than expected, we will have continued institutional support and funding to extend our enrollment period. We will partner with GetWell Loop, an organization that has been well established within our hospital system, to develop a custom build for our application. We will evaluate our outcomes based on an intention-to-treat and per-protocol analysis and will define statistical significance as a p-value <0.05.

STU#:

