**Figure 1: Experimental design**

The primary study aim is to improve patient satisfaction, education, and patient reported outcome measures after urethroplasty. All enrolled patients will complete a urethroplasty specific PROM survey, the Urethral Stricture Specific PROM (USS-PROM), as well as the Patient-Reported Outcomes Measurement Information System 29-item profile (PROMIS-29 v2.0) preoperatively, two weeks after catheter removal, and again at three months after surgery. Three months after surgery patients will also complete a decision regret scale. Patients in the control arm will receive surveys at the specified timepoint via RedCap. No additional visits will be required. Patients enrolled with the application will complete an overall assessment of GetWell Loop at the end of the study. This is administered in the application.

The second aim of the study is to decrease patient phone calls and messages due to improved patient education and troubleshooting provided by the interactive guide. Prospective chart review will be conducted on all patients enrolled in the study to evaluate the number of MyChart messages and phone calls.

The final aim is to decrease emergency department visits and improve postoperative outcomes. Postoperative complications will be rated on the Clavien-Dindo classification. Emergency department visits will be assessed by prospective chart review and patient interviews. Overall healthcare costs will be extrapolated based on the outcomes of emergency department visits.

DATA AND SPECIMEN BANKING

All data from GetWell Loop will be stored anonymously with unique patient identifiers in the GetWell Loop storage cloud, which can be downloaded remotely by the research team. Data will then be compiled and prospectively maintained in an encrypted

STU#:

REDCap database through our institution. Data will be accessible only to authorized members of the study team. Data will be kept indefinitely. For subjects agreeing to the future use of their data in institutionally approved studies not yet identified, data, either de-identified or identifiable, will be provided to future investigators as stipulated and approved in their IRB application and data security plan.

SHARING RESULTS WITH PARTICIPANTS

Results from the study and from the GetWell mobile health platform will be shared in person during the patient's follow-up at the completion of the study.

STUDY TIMELINES

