The duration of the study is 12 months, however participation for each patient will be from time of their clinic visit where they sign up for urethroplasty and are recruited into the study to 90 days following their surgery. We plan to enroll 80 patients (40 per arm) and estimate this will take the entire year given our current clinical patient volume. We plan to start enrolling patients in August 2023 in anticipation of initiating launch of the application in August 2023. We anticipate completion of the participation in the study around July 2024.

INCLUSION AND EXCLUSION CRITERIA

Eligible patients include those over 18 years old who have a urethral stricture and are undergoing urethroplasty surgery with [name] at Northwestern Memorial Hospital. Exclusion criteria consists of patients without mobile phone capability to utilize GetWell Loop, physical or cognitive impairment precluding usage of a mobile phone or answering questionaries, and inability to consent to the study.

VULNERABLE POPULATIONS

PARTICIPANT POPULATION(S)

Accrual Number:	Category/Group: (Adults/Children Special/Vulnerable Populations)	Consented: Maximum Number to be Consented or Reviewed/Collected/Screened	Enrolled: Number to Complete the Study or Needed to Address the Research Question
Local	Adults	120	80
Study-wide		120	80
Total:		120	80

STU#:

RECRUITMENT METHODS

Patients scheduled to undergo urethroplasty surgery will initially be approached in clinic and given information regarding the study design and goals. All patients regardless of race/ethnicity/gender/socio-economic status will be approached. If patients have transportation issues and cannot make it to an in-person visit, a virtual visit can be offered instead, and patients can be recruit via this approach. If interested, the patient will then sign a generalized consent form enrolling them into the study. Eligible patients will then be randomized to one of two arms: standard care pathway and mHealth pathway. We will attempt to match patients based on demographics to have even distributions between the groups. We will utilize non-blinded block randomization technique due to the nature of the intervention pathway and need for continuous enrollment.

COMPENSATION FOR PARTICIPATION IN RESEARCH ACTIVITIES

To reduce attrition, financial incentive will be provided after completion of the 3-month follow up surveys with a \$100 Amazon gift card.

WITHDRAWAL OF PARTICIPANTS

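### Satisfaction is named first in the primary endpoint, but no instrument given to both arms is designated to measure it

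*Protocol*

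**What the plan says.** The protocol's Study Endpoints section reads "Primary endpoint: Improve patient satisfaction, education, and patient reported outcome measures after urethroplasty". Satisfaction is also in the title, the objective and Aim 1.

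Aim 1, repeated under Procedures Involved, lists the patient-reported instruments. All enrolled patients complete a stricture-specific survey and the "Patient-Reported Outcomes Measurement Information System 29-item profile (PROMIS-29 v2.0) preoperatively, two weeks after catheter removal, and again at three months after surgery". Then: "Three months after surgery patients will also complete a decision regret scale", with no restriction to one arm. On delivery, Procedures Involved says "Patients in the control arm will receive surveys at the specified timepoint via RedCap".

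The last instrument is different: "Patients enrolled with the application will complete an overall assessment of GetWell Loop at the end of the study". Procedures Involved adds "This is administered in the application".

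On timing, Recruitment Methods says "Patients scheduled to undergo urethroplasty surgery will initially be approached in clinic and given information regarding the study design and goals". Randomisation follows consent.

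**The concern.** A randomised trial that sets out to improve satisfaction needs a satisfaction measure taken in the same way in both arms. The protocol names the outcome but does not say which instrument carries it. The instrument closest in spirit rates the product and has no control-arm counterpart.

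At stake is one of the three named parts of the primary endpoint. If both arms do not complete a suitable item, no later analysis can supply it. A statistical analysis plan can say which collected instrument serves which part of the endpoint, but it cannot create ratings that control patients were never asked for. The background section itself says that earlier urology app studies were feasibility studies without comparison to standard care. An app rating from one arm would be evidence of that same kind.

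**Working it through.** This is mainly a check of which instrument goes to which arm. The planned size is 40 per arm (Procedures Involved), and 2 × 40 = 80 agrees with the stated total. The protocol gives no effect size, standard deviation or power, so 80 cannot be reproduced as a power calculation.

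| Instrument | When | Maximum ratings, app v control | Tied to satisfaction in the protocol? |
|---|---|---|---|
| Stricture-specific survey | Before surgery, two weeks after catheter removal, three months | 40 v 40 | No |
| PROMIS-29 v2.0 | Same three times | 40 v 40 | No |
| Decision regret scale | Three months | 40 v 40 | No |
| GetWell Loop assessment | End of study, inside the app | 40 v 0 | No |

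**GetWell Loop assessment.** With no control ratings, a between-arm difference cannot be estimated at any sample size or significance level. To illustrate with assumed figures, suppose 90% of app patients gave a favourable rating. If 70% of controls would have done so on a comparable question, the difference is 90 − 70 = 20 points. If 90% would have, it is 90 − 90 = 0. The app-arm figure alone cannot separate the two.

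**Decision regret.** This can be compared between arms. For context, assume a two-sided 5% level (the protocol states p < 0.05 without sidedness), SD = 1 and no dropout, and use the normal approximation for two means.

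- Detectable difference = (z for 1 − α/2 + z for power) × √(2/n).
- 80% power: (1.960 + 0.842) × √(2/40) = 2.802 × 0.2236 = 0.63 SD.
- 90% power: (1.960 + 1.282) × 0.2236 = 0.72 SD.
- Power at a true difference of 0.3, 0.5 and 0.8 SD is about 27%, 61% and 95%.

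So the scale supports a real contrast, although only fairly large differences would be detected reliably. The open question is what it measures. Study Timelines starts participation at the clinic visit where the patient signs up for surgery, and Recruitment Methods describes those approached as already scheduled. App training comes only after randomisation. If the scale asks about the decision to have urethroplasty, that decision came before allocation.

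**Stricture-specific survey.** Aim 1 calls it USSIM and Procedures Involved calls it USS-PROM. The items of neither are in the protocol, so whether one of them asks about satisfaction cannot be settled from the document.

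**The case against.** The strongest reply is that a satisfaction-related measure is already collected in both arms. Decision regret is taken three months after surgery and can reflect the whole perioperative experience. Because allocation is randomised, its between-arm difference is a valid contrast even though the decision came earlier. The protocol speaks of satisfaction after urethroplasty and does not limit this to satisfaction with care or teaching, so regret and the outcome surveys may bear on it. The stricture survey may also contain a satisfaction item.

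Most of this stands, and it rules out three stronger readings.

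- A reader might infer that the trial cannot compare satisfaction between arms at all. The documents do not support that, because regret is a related measure available in both arms and the survey items are not shown.
- A reader might infer that the app cannot affect regret. That is not established either: the wording of the scale is not given, and the app delivers content both before and after surgery.
- A reader might infer that the investigators mean to rest a satisfaction claim on the app-arm rating. The protocol does not say so.

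The reply does not supply the missing designation. The endpoint lists satisfaction apart from the patient-reported outcome measures, and no instrument is named as carrying it. A separate analysis plan could close the gap only if a suitable item is already being collected from both arms.

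**Conclusion.** The point holds as a gap in the definition and collection of one of the three named parts of the primary endpoint. No both-arm instrument is described as measuring satisfaction or designated to do so. The GetWell Loop assessment gives up to 40 ratings against 0 and can only be descriptive. Decision regret gives up to 40 against 40 but has no stated link to satisfaction.

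This should be fixed, but it does not undermine the trial as a whole: the patient-reported outcome part of the endpoint is measured in both arms. The conclusion rests on the instruments as listed in Aim 1 and Procedures Involved. It would narrow to a matter of naming if the stricture survey proves to contain a suitable satisfaction item.

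**What to change.** Add one short rating of satisfaction with perioperative information and care to the existing three-month survey. Use identical wording in both arms, with no mention of the app, and name it in the protocol as the satisfaction measure. If an instrument both arms already complete contains a suitable satisfaction item, name that item instead.

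Keep the GetWell Loop assessment as a descriptive result for the app arm, and report decision regret as its own outcome. If no both-arm satisfaction measure is named, remove satisfaction from the primary endpoint and from the conclusions.

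Adding the rating costs a protocol amendment and about one minute of survey time per patient, with no extra visit. Naming an existing item adds no patient time. The change helps only patients whose three-month survey is still to come, so it should be made early.

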Statistical outcomes will be analyzed based on intention-to-treat and per-protocol analysis. We will define statistical significance as p-value <0.05. With guidance from an institutional biostatistician, we will perform statistical analysis using R (R Foundation for Statistical Computing, Vienna, Austria) comparing all two study arms. After enrollment into the study, patients will be followed for a 90-day period. Data from the standard care pathway will be collected in person or during telehealth visits. All data from GetWell Loop will be stored anonymously with unique patient identifiers in the GetWell Loop storage cloud, which can be downloaded remotely by the research team. Data will then be compiled and prospectively maintained in an encrypted REDCap database through our institution. The confidentiality and privacy rights of all subjects enrolled in the study will be fully protected and HIPAA regulations will be strictly enforced. Data resulting from this study will not be linked to subjects. Subjects will not be referred to by name or initial in any publications.

PROVISIONS TO MONITOR THE DATA TO ENSURE THE SAFETY OF PARTICIPANTS

Only members of the research team and individuals who may have access to medical records and/or informed consent documents due to their job function at the participating sites may access the records.

PROVISIONS TO PROTECT THE PRIVACY INTERESTS OF PARTICIPANTS

No identifiable information about the patient, or provided by the patient, during the research, will be disclosed to, except:

- If necessary to protect subjects' rights or welfare (for example, if they are injured and need emergency care); or
- When the Collaborative Northwestern Institutional Review Board monitors the research or consent process; or
- When the Office for Human Research Protections (OHRP), the Office of Research Oversight (ORO), or other governmental regulatory agencies monitor the research; or if required by law.

The risk of the breach of confidentiality is possible in this study. However, all precautions will take place to make sure this issue is avoided. Data collected by study coordinators will be maintained in a secure server maintained by Northwestern University. The names of the patients will not be included on the primary database, but they will be followed by an ID number. When the results of the research are published or discussed in conferences, no information will be included that would reveal patients'

STU#:

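### Aim 2 counts phone calls and MyChart messages only, so care messages sent in GetWell Loop drop out of the count in the app arm alone

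*Protocol*

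**What the plan says.** Aim 2 (Objectives) states its purpose thus: "The second aim of the study is to decrease patient phone calls and messages due to improved patient education and troubleshooting provided by the interactive" (the sentence closes by naming the in-app guide). The measurement follows directly: "Prospective chart review will be conducted on all patients enrolled in the study to evaluate the number of MyChart messages and phone calls". Procedures Involved repeats both sentences. Study Endpoints lists the secondary endpoint as "decrease patient phone calls, chart messages, ER visits, and improve complication rates". All three places name the channels, and none names GetWell Loop.

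The description of the intervention adds a channel. Under Participant/user support: "Participants will be able to message providers with questions regarding the app or regarding their care through GetWell Loop and via Epic myChart". Under Risks related to app use, a study team member receives notifications from a secure messaging portal, and then: "Patients will also have the option to ask care-related concerns through Epic MyChart". MyChart is thus presented as a route beside the portal.

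On data capture, Privacy and confidentiality protections says: "Research data including patient demographic, survey and medication adherence data will be collected in GetWell". Messages are not named there.

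**The concern.** The channel that is not counted exists in one arm only. Control patients can phone or use MyChart, and both are counted. App patients can phone, use MyChart or write in GetWell Loop, and the third is not counted. If some app patients put their care questions in the app, the counted total falls even when patients ask just as many questions and providers answer just as many.

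Aim 2 attributes the expected fall to better teaching and the interactive guide. A count that also falls when a question changes inbox cannot support that reading. The opposite distortion is possible too: questions about the app itself, sent by MyChart or phone, arise only in the app arm and raise its count. At stake is the contact component of the secondary endpoint, and with it the whole of Aim 2.

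**Working it through.** **1. The channels side by side**

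| Channel | Control arm | mHealth arm | Counted under Aim 2? |
|---|---|---|---|
| Phone | yes | yes | yes |
| MyChart | yes | yes | yes |
| GetWell Loop message | no | yes | not stated; not named in the measurement rule |

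That only the mHealth arm has the app follows from Participant/user support (training is for those randomized to mHealth) and Procedures Involved (controls receive their surveys through REDCap).

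**2. Expected direction**

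Let both arms have the same true mean number of contacts, *m*. Let *s* be the share of app-arm contacts moved into GetWell Loop. Let *a* be the app-related queries arriving by phone or MyChart, as a fraction of *m*. The counted ratio, app to control, is

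(1 − s) + a.

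- s = 0.10, a = 0: 0.90
- s = 0.25, a = 0: 0.75
- s = 0.50, a = 0: 0.50
- s = 0, a = 0.10: 1.10
- s = 0.25, a = 0.10: 0.85
- s = 0.50, a = 0.10: 0.60

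The true ratio is 1.00 throughout.

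**3. How often this would look significant**

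The Protocol gives no power, rate or standard deviation for Aim 2, so there is no figure of its own to reproduce. It fixes 40 patients per arm (Procedures Involved) and a 0.05 significance level (Data Management and Confidentiality). Everything else here is assumed, including a two-sided test.

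*Simulation.* Negative binomial counts with mean 3, 5 or 8 and dispersion k = 0.5, 1 or 2; app-arm counts thinned binomially by (1 − s); two-sided Mann-Whitney test; 4,000 replicates in each of the nine combinations. Ranges are over the combinations.

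| Diverted share s | Rejection, a = 0 | Rejection, a = 0.10 |
|---|---|---|
| 0 | 4.2-5.2% | 8.9-13.6% (at most 0.7% in favour of the app) |
| 0.05 | 4.8-5.9% | not run |
| 0.10 | 5.2-8.1% | not run |
| 0.25 | 9.3-30.1% | 4.5-11.1% |
| 0.50 | 34.1-92.4% | 8.8-68.7% |

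With the heaviest overdispersion (k = 0.5) and a = 0, rejection is 9.3-9.8% at s = 0.25 and 34.1-36.3% at s = 0.50.

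*Cross-check by normal approximation.* The counted difference is m·s, and SD = √[(c·m + c·m(1 − s))/2], where c is the variance-to-mean ratio. For m = 4, s = 0.30, c = 3: difference 1.2; SD = √[(12 + 8.4)/2] = 3.19; standard error = 3.19 × √(2/40) = 0.714; 1.2/0.714 = 1.68; chance of a falsely significant reduction = Φ(1.68 − 1.96) = 39%. The other results for m = 4 are:

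| s | c = 1 | c = 3 |
|---|---|---|
| 0.10 | 15% | 8% |
| 0.20 | 47% | 19% |
| 0.30 | 83% | 39% |
| 0.50 | >99% | 85% |

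Over m = 2 to 6, s = 0.20 gives 12-64% and s = 0.30 gives 22-95%.

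These are generally higher than the simulated figures because the assumed spread is smaller. In the simulation the variance-to-mean ratio is 1 + m/k, from 1 + 3/2 = 2.5 to 1 + 8/0.5 = 17, against 1 to 3 here. Both models agree on direction and on the steep rise with s; neither fixes the size.

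**The case against.** **In-app messages might already be counted.** The endpoint speaks of chart messages, measured by chart review, and the Protocol does not say whether GetWell Loop messages are filed in Epic. If they were filed, a reviewer might count them. The silence is real, but the text treats the two as separate channels, and the measurement sentence names MyChart. A copied message would still need a rule to count.

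**The data list is not exhaustive.** This stands: the list opens with an inclusive word, and elsewhere all GetWell Loop data are said to be downloadable by the team. So the Protocol does not show that messages are unobtainable. It only fails to plan for them, which makes the fix look feasible.

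**Counting rules belong in the SAP.** True of such details as how to classify technical queries. But the channels to be counted are fixed in the Protocol in three places, and an SAP cannot analyse messages that were not collected.

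**Diversion may be small.** This also stands. The portal is described in terms of weekly monitoring, with MyChart offered for care questions, so in-app messaging may prove a minor route. Vendor support takes app-technical problems, so the 10% offset is purely an assumption.

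**Phone and MyChart traffic is a legitimate workload measure in itself.** Agreed. The count as defined validly estimates the effect on those two channels. It does not estimate the effect on the number of questions patients ask, which is how Aim 2 explains the fall.

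**Conclusion.** The concern holds. As written, the Aim 2 count omits a care-contact channel that only the mHealth arm has, and no passage says that channel is counted some other way. The textual mismatch is certain; the amount of bias is not, because the Protocol gives no contact rate, dispersion, diversion share or test.

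Under the assumed count models, diversion of up to about 10% does little harm in the simulation. At 25% the false-positive rate may reach 30%, and at 50% it may reach 92%. App-related queries in the counted channels can offset part of this or, with no diversion, tilt the result against the app. Either way, the difference cannot be read as the app's effect on patients' questions. This should be fixed, but it concerns one component of the secondary endpoint. The primary endpoint, emergency visits and complications are not touched.

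**What to change.** In Aim 2, Study Endpoints and Procedures Involved, define the outcome as the total number of patient-initiated, care-related contacts per patient: phone calls plus MyChart messages plus GetWell Loop messages to providers. Report each channel separately beside the total. Exclude app-technical queries by one written rule applied to all three channels. Add GetWell Loop message counts to the data collected.

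State one counting window for both arms, from enrolment/randomization to 90 days after surgery, so that preoperative contacts count. It has to be explicit because Study Timelines says "participation for each patient will be from time of their clinic visit where they sign up for urethroplasty" and ends it 90 days after surgery, whereas Data Management and Confidentiality says "After enrollment into the study, patients will be followed for a 90-day period". That inconsistency applies to both arms and is not a source of the bias described here, but the outcome cannot be counted until it is reconciled.

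The cost is one sentence in each of the three places and a message export linked to the study ID. Availability must be confirmed, since messages are not named among the GetWell data and records are held under non-identifying codes. When true contact is equal, the full care-related count brings the expected ratio back to 1.0 and the false-positive rate to about 5%. No stated sample size or power figure changes.

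There are two downsides. The apparent effect may shrink, and easy in-app messaging may generate extra contacts that count against the app. The channel breakdown shows those extra contacts but does not remove them.
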